Second-Line Uterotonics in Postpartum Hemorrhage: A Randomized Clinical Trial

NCT: 03584854

April 04, 2018

*Biostatistical Analysis Plan*

An a priori power analysis determined that enrollment of 37 patients per group would provide 80% power at a 2-sided alpha level of 0.05 to detect a 1-point difference, with estimated within-group standard deviation of 1.5, in mean uterine tone at 10 minutes after study drug administration using a two-sample t-test. Randomization of 100 patients was planned to account for protocol violations. Uterine tone at 10 minutes (primary outcome) and 5 minutes (secondary outcome) after study drug administration were compared between groups with adjustment for baseline tone and trial site using the generalized estimating equations (GEE) method with an identity link to account for the correlation between repeated measurements on the same patient. The primary analysis was a complete-case analysis, where 3 patients (3%) missing uterine tone at baseline and/or 10 minutes were excluded from the analysis. A multiple imputation sensitivity analysis was also performed which used the multivariate imputation by chained equations approach to impute missing uterine tone values using observed tone measurements (baseline, 5, and 10 minutes), parturient characteristics (age, race, BMI, parity), infant characteristics (number of fetuses, infant birth weight), trial site, interventions (randomized study drug, administration of second study drug, intraoperative transfusion), and outcomes (intraoperative blood loss, change in hematocrit from baseline to 24 hours post-delivery) to create 10 complete datasets. The primary outcome was compared in each of the 10 imputed datasets, and results combined using Rubin's rule.

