All continuous secondary outcomes were initially assessed for the normality of residuals from a multivariable linear regression model with trial site and baseline uterine tone as covariates. Outcomes displaying normally distributed model residuals were analyzed using multivariable linear regression, with effect size presented as adjusted difference in means with 95% CI. Outcomes with all non-zero values that displayed skewed linear regression model residuals were natural log-transformed and analyzed using multivariable linear regression, with effect size presented as adjusted ratio of geometric means with 95% CI. Outcomes containing at least one zero value that presented skewed linear regression model residuals were compared between groups using multivariable quantile regression, with effect size presented as adjusted difference in medians with 95% CI.

All binary outcomes were initially considered for comparison using multivariable logistic regression (for single measurements) or generalized estimating equations with a logit link (for repeated measurements) with trial site and baseline uterine tone as covariates. If the multivariable regression converged, effect size was presented as adjusted odds ratios with 95% CI. If the model did not converge due to low incidence, groups were compared using a Fisher's exact test and effect size presented as risk difference with exact 95% CI.

Time to receive second study drug was compared between groups using a multivariable Cox proportional hazards model, with effect size presented as adjusted hazard ratio with exact 95% CI. Complete-case analysis was performed for all secondary outcomes. All analyses were performed using SAS software version 9.4 (SAS Institute, Cary, NC).

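### Complete-case secondary models adjusted for baseline tone drop a woman whose outcome was observed if her 0-minute score is missing (0 to 3 of 100 women)

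*SAP*

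**What the plan says.** For continuous secondary outcomes, the SAP first checks the "normality of residuals from a multivariable linear regression model with trial site and baseline uterine tone as covariates". Outcomes that pass are analysed by linear regression. Skewed outcomes without zeros are log-transformed and analysed by linear regression. Skewed outcomes with zeros "were compared between groups using multivariable quantile regression, with effect size presented as adjusted difference in medians with 95% CI". The last two models are called multivariable and their effects adjusted, but their covariates are not listed again.

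All binary outcomes start with logistic regression or, for repeated measurements, "generalized estimating equations with a logit link (for repeated measurements) with trial site and baseline uterine tone as covariates". There is one exception: "If the model did not converge due to low incidence, groups were compared using a Fisher's exact test". That test has no covariates.

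For the second study drug, the SAP says: "Time to receive second study drug was compared between groups using a multivariable Cox proportional hazards model". It names no covariates there.

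The missing-data rule follows: "Complete-case analysis was performed for all secondary outcomes". For the primary outcome the analysis is also complete-case, "where 3 patients (3%) missing uterine tone at baseline and/or 10 minutes were excluded from the analysis". A multiple-imputation sensitivity analysis imputes missing tone scores, but only the primary outcome is compared in the imputed datasets.

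Protocol Section VI requires trial site in all models and does not name baseline tone.

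**The concern.** A regression adjusted for baseline tone cannot use a woman without a baseline score. With a complete-case rule she is removed from the comparison even when her outcome is known.

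The secondary outcomes do not depend on that score. Under Protocol Section V, obstetric physicians and nurses document blood loss. Transfusion, interventions, vasopressors and length of stay are recorded separately. Side effects come from blinded interviews and the medical record. One blank on the intraoperative tone sheet can therefore discard data that were collected independently of it.

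The imputed tone values that could keep her are not used for these outcomes. The trial plans only 100 randomised women, and some safety outcomes may have few events, so each observed outcome is worth keeping if that costs little.

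**Working it through.** **Inputs.** From the SAP: 100 women planned; 3 women (3%) missing baseline and/or 10-minute tone; covariates and complete-case rule as above; design difference 1 point, SD 1.5, 37 per group. From Protocol Section VI: difference 1.2, SD 1.9.

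**1. The plan's own figures.** 3/100 = 3.0%, as stated. The SAP gives no number actually randomised. Totals from 86 to 119 also round to 3% (3/86 = 3.49%, 3/119 = 2.52%), so 100 is used as an assumption. A two-sample t-test with difference 1, SD 1.5, two-sided 0.05 and 80% power needs 36.3 per group, which rounds up to the SAP's 37 (power 80.8% at 37, 79.7% at 36).

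**2. Who is dropped.**

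| Tone score missing | Model adjusted for baseline tone | Fisher's test |
|---|---|---|
| 0-minute only | dropped | kept, unless the set is restricted |
| 10-minute only | kept | kept |
| both | dropped | kept, unless the set is restricted |

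The number lost equals the number without a 0-minute score. Because the three women are not split, this is 0, 1, 2 or 3.

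**3. Check of the mechanism.** In simulated data with 100 rows and three blank baseline scores, linear, quantile and logistic models with baseline tone each used 97 rows. The linear model without baseline tone used 100, as did the linear model with blanks filled by the mean. The two-by-two table for Fisher's test also held 100.

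**4. Precision.** With m women lost, the standard error is multiplied by √(100/(100 − m)):

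- m = 1: 1.005
- m = 2: 1.010
- m = 3: 1.015

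If all three come from one arm of 50, the factor is √[(1/50 + 1/47)/(1/50 + 1/50)] = √(0.04128/0.04) = 1.016. Over the totals compatible with 3%, the factor for m = 3 runs from √(119/116) = 1.013 to √(86/83) = 1.018.

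**5. Scale in power.** The documents give no design assumptions for the secondary outcomes, so the primary ones serve as a yardstick. Going from 50/50 to 50/47, t-test power falls from 91.0% to 90.1% (difference 1, SD 1.5), and from 87.8% to 86.8% (difference 1.2, SD 1.9).

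**6. Sparse events.** Assume 6/50 v 0/50: Fisher p = 0.027. If three women with events were dropped, 3/47 v 0/50 gives p = 0.11. This is an extreme bound. It is also a case the SAP would handle differently: with no events in one arm the logistic estimate for drug does not exist, so the outcome goes to Fisher's test, where those women stay unless the complete-case set is imposed.

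**The case against.** A reader might infer that the rule removes women from all transfusion and safety comparisons, and that it could take out a large share of rare events. With an assumed 4 to 6 events, losing 1 to 3 of them would be 1/6 = 17% to 3/4 = 75%. The documents do not support that. They give no event counts. They do not show that any woman lacked a 0-minute score. The 75% figure needs three such women, all with the same event, only four events in total, and a model that still converged. The sparsest outcomes are also those most likely to reach Fisher's test.

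A reader might also assume that the 0-minute score is missed most often in the most urgent cases. That is a guess. Protocol Section V has the score requested when the drug is given, before the timer is set. The 10-minute score falls later, during continuing management, and may be missed at least as easily. Missing it does not trigger this loss.

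The primary analysis is not left unprotected either. Its multiple-imputation sensitivity analysis restores the excluded women, and the SAP already reports how many are missing, so changing the primary model now would be post hoc.

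These objections limit the size and reach of the point. They do not remove it. The fallback depends on non-convergence, not on rarity alone, so a sparse outcome whose model converges stays in the adjusted analysis. The SAP also does not say which women enter Fisher's test, so the set analysed can change with the convergence of each model.

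**Conclusion.** The point holds within limits. For secondary outcomes analysed by a regression adjusted for baseline tone, the complete-case rule drops a woman whose outcome was observed but whose 0-minute score is missing. This is stated for binary outcomes and for the starting linear model of continuous outcomes. It is inferred for the log-linear and quantile models, and open for the Cox model.

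The loss is 0 to 3 of 100 women. With 100 randomised, the standard error rises by at most about 1.5% (1.6% if all three are in one arm). Any larger effect on sparse events is an unquantified possibility. The fallback to Fisher's test adds an inconsistency: the same woman may be kept for one outcome and dropped for another.

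This is a modest improvement, worth making because it is cheap. It is not evidence that the results are biased.

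**What to change.** In the secondary models, replace a missing baseline tone by the mean at the woman's site, pooled over both arms, so that every randomised woman with an observed outcome is analysed. Use the same women for Fisher's test. Keep the complete-case result as a sensitivity analysis. Name the covariates of the log-linear, quantile and Cox models, report the number analysed per arm for each outcome, and align Protocol Section VI with the SAP on baseline tone.

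Pooling over arms keeps the filled value independent of assignment. The score is rated as the drug is given, by an obstetrician meant to be blinded, so the randomised comparison is preserved.

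The site mean is simpler than reusing the existing imputations. Those would need each secondary model fitted in 10 datasets and combined, and their imputation model leaves out most of the safety outcomes.

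Leave the primary analysis as it is. The 5-minute tone score is fitted in the same GEE model and stays with it.

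The cost is a few SAP sentences and a rerun of the secondary models. Single mean filling slightly weakens the covariate adjustment, for at most 3 women.
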